## **C. Summary of Changes**

### **Appendices:**

I: Trial Variable Table

II: Intake Survey

III: Exit Survey

TRIAL OVERVIEW Title	Comparative Effectiveness of Financial Incentives and Nudges to Reduce Cellphone Use While Driving Among UBI Auto Policy Holders (PUT-IT-DOWN Study)
Clinical Trials Number	NCT03833219
Sources of monetary or material support	FHWA
Study Sites	National cohort of Progressive Snapshot Mobile auto insurance policy holders
Conditions studied	Distracted driving
Interventions	Push notification reminders, social comparison feedback, and financial incentives
Comparator	Self-monitoring (control)
Inclusion criteria	
Progressive Snapshot Users with policy activated within recruitment period
 
Progressive Snapshot policy holder in one of the following states and regions: MI, PA, TX, FL, TN, OR, GA, NE, OK, OH, MT, MO, NV, CT, WI, MD, KY, MN, NH, NJ, AZ, ME, LA, SC, CO, MS, IN, IA, AL, ND, UT, RI, WV, WY, IL, AR, DE, KS, SD, NM, VT, ID, and the District of Columbia
 
Has an email address

Exclusion criteria	
 
1. Progressive Snapshot Mobile App not updated to enable push notifications
 
2. Customer's residential address is in a state in which phone use while driving is factored into insurance rating
 
3. Customer's Snapshot Mobile App does not collect trip data with all sensors active
 
4. Customer in Snapshot program for < 30 days or more > 70 days
 

Study type	
Interventional
 
Phase 1: Baseline – 30-70 days (usual care monitoring in Snapshot program)
 
 
• Phase 2: Intervention - 50 days – delivered to customers who agree to participate
 
• Phase 3: Post-intervention - remaining time until Snapshot rating complete (~30-60 days).
 

Randomization Arms	
 
1. Control (monitor only)
 
2. Social comparison feedback
 
3. End of rating period incentive
 
4. End of rating period incentive + social comparison feedback
 
5. Weekly loss-framed incentive + social comparison feedback
 

6. Larger weekly loss-framed incentive + social comparison feedback

Target sample size	3000 Participants 500 participants per study arm.
Primary outcome	Percent of trip time engaged in active handheld phone use (also measured as seconds of handheld phone use while driving per hour of driving)

## 1. Background and Significance

### 1.1 Scope of Problem

The proportion of U.S. drivers witnessed visibly manipulating hand-held devices while driving has doubled since 2010 (NHTSA 2014), despite the fact that 97% of Americans know this is dangerous (AT&T 2012) and texting while driving is illegal in all but four states. Current policies to curb cellphone use while driving have had limited impact because they do not address the underlying impulsivity (Hayashi, 2015) that causes drivers to continue to engage in this behavior despite knowing it is against their best interests (Delgado 2016).

### 1.2 Existing Interventions

In November 2016, NHTSA released guidelines recommending the use of operating systems, aftermarket applications, and devices to enable a “driver mode” on smartphones to limit use while driving (Department of Transportation 2016). Akin to the federally mandated use of an “airplane mode” intended to limit cellular transmissions during air travel, a driver mode can be implemented on cellphones automatically limiting handheld cellphone use over certain speed thresholds consistent with driving based on native phone sensors or Bluetooth pairing with in-vehicle devices. These settings and applications have customizable configurations that can be programmed to activate when the car is moving, including locking the phone screen, silencing notifications, blocking incoming calls and text messages, and sending automated responses to incoming text messages. Research on these applications supports the efficacy of blocking technology on significantly reducing phone calls and text messaging while driving compared to control groups (Creaser et al. 2015; Ebel et al. 2015; Funkhouser and Sayer 2013). Third-party smartphone applications that enable a driver mode are also available for download (“Using Technology” 2014), but adoption and use have been limited. Though reasons for limited adoption have not been examined in the peer-review literature, media reports suggest that this is due to limited consumer acceptability (Richtel 2016). A recent study examining the adoption of similar smartphone apps to monitor and provide feedback on driving behavior among young drivers showed that perceived gains (e.g., financial incentives) and social norms are the biggest motivating factors in adoption of these applications. June 5, 2017, Apple (Cupertino, CA) announced a “do not disturb while driving mode” that became available as an iPhone operating system feature in Fall 2017 that can be turned on to lock the phone screen and silence and send automated responses to incoming text messages while driving (Sinder 2017).

Applications and settings aimed at limiting cellphone use while driving will only be effective from a population health standpoint if widely adopted and sustainably used. A promising approach to increased adoption of these applications and settings to sustainably change behavior is to increase perceived gains of these actions by providing financial incentives (Kervick et al. 2015; Musicant and Lotan 2016). This could be brought to scale through usage-based auto insurance programs that use mobile telematic smartphone apps to provide insurance discounts based on monitored driving and phone use behavior (Delgado et al. 2016). The effectiveness of financial incentive strategies in usage-based insurance programs could be enhanced by leveraging insights from behavioral economics, as has been effective for

health behavior change (Delgado et al. 2016). This includes increasing the frequency and salience of incentives, to be more averse to losses than to gains. (Asch and Rosin 2016; Loewenstein et al. 2007, 2013). Despite the promise of redesigning usage based insurance programs with insights from behavioral economics, such strategies have not been tested previously.

### **1.3 Behavioral Drivers of Vehicle Safety**

Conventional behavior change models assume individuals form behavioral change intentions based on the rational assessment of the costs and benefits and consistently act in their own interest. By contrast, behavioral economics applies psychological insights to understand the many natural decisions people make that routinely deviate from their best interests. Through dozens of studies, we have demonstrated how a variety of common decision errors such as status quo bias, present bias (tendency to overweight immediate costs and benefits over future), loss aversion, regret aversion, and social norms, can be used to develop effective, high impact interventions for health behavior change. Our work has led to the development of a new health plan (Humana Simplicity), the enrollment process for automatic medication refills at CVS Health, financial incentives and smoking cessation programs among employees at General Electric and CVS. Further translating our deep expertise in behavioral economics to reducing cellphone use while driving could lead to a transformational paradigm shift in the approach to behavior change for this emerging cause of injury and risky driving in general.

### **1.4 Rationale for financial incentive and social comparison interventions**

We have designed the interventions to be tested in our field experiment with several elements based on behavioral economic theory (Lowenstein, Volpp 2007), including: (1) promoting restraint from using a cellphone while driving by providing a substitute reinforcer in the form of incentives; (2) delivering incentives on a weekly basis to offset a heightened tendency to favor immediate gratification over delayed benefits among those who engage in texting while driving; (3) providing feedback via smartphones regarding accrued losses from non-adherence to maximize regret aversion; (4) framing reward-based incentives as losses to augment motivation through loss aversion; leveraging; and (5) social network theory and evidence that behavior change programs may be more effective when individuals are compared to those similar to them.

## **2. TRIAL DESIGN**

### **2.1 Overview**

We propose to conduct a randomized, control trial evaluating the comparative effectiveness of social comparison and financial incentive interventions with customers of Progressive's mobile phone usage-based insurance policy. A total of 3,000 adult participants will be enrolled with 500 participants per arm. We expect an attrition rate of 17% based on historical customer data.

### **2.2 Setting**

The study will be conducted by Progressive Insurance and their mobile technology vendor TrueMotion. Progressive will be responsible for recruiting participants from their newly enrolled group of Snapshot customers. TrueMotion will be responsible for conducting study procedures including interventions, data collection, and participant payments. Penn researchers will be responsible for study design and data analysis.

### **2.3 Inclusion Criteria**

#### **Inclusion Criteria:**

1. Progressive Snapshot Users with policy activated within recruitment period

2. Progressive Snapshot policy holder in one of the following states and regions: MI, PA, TX, FL, TN, OR, GA, NE, OK, OH, MT, MO, NV, CT, WI, MD, KY, MN, NH, NJ, AZ, ME, LA, SC, CO, MS, IN, IA, AL, ND, UT, RI, WV, WY, IL, AR, DE, KS, SD, NM, VT, ID, and the District of Columbia

3. Has an email address

**Exclusion Criteria:**

1. Progressive Snapshot Mobile App not updated to enable push notifications
2. Customer's residential address is in a state in which phone use while driving is factored into insurance rating
3. Customer's Snapshot Mobile App does not collect trip data with all sensors active
4. Customer in Snapshot program for < 30 days or more > 70 days

## **2.4 Participant Identification**

Progressive will designate a cohort of customers eligible, based on inclusion and exclusion criteria, to invite to participate based on being in the Snapshot program on Day 30 to 70 at the date of study invitation.

## **2.5. Consent Procedures**

Progressive Snapshot users will be sent an email from Progressive about participating in research. Those interested will follow a link that takes them to a website hosted by TrueMotion with information about participating in the study. Those that wish to participate will opt-in to enroll online through the website hosted by TrueMotion and complete an intake survey.

## **2.6. Contact Information**

The research team and technology team at the University of Pennsylvania and TrueMotion (TMO), respectively, will not have access to participant information. Progressive will send invites with a Globally Unique Identifier (GUID) attached to the enrollment link. Progressive will send a list of GUIDs to TMO who will use these GUIDs to identify participants. TrueMotion will pair those GUIDs with participant emails that are given by the participant during the enrollment process. When participants enroll in the study, on the website hosted by TrueMotion, they will have to provide their e-mail address to receive their compensation. TrueMotion will use the email addresses provided by participants to compensate those that complete study surveys or are in a treatment arm that receives monetary incentives. Participants that have any issues or concerns during the study will be prompted to contact the study team via email at [[contact]](mailto:[contact]).

## **2.7. Baseline**

All new Progressive Snapshot customers will be monitored for 30-70 days during the baseline period. Progressive will designate a cohort of customers to invite into the study who will be on day 30-70 of their Snapshot monitoring period on the date of invitation. Study participants will be those that opt-in after the baseline period.

## **2.8. Baseline Assessment**

### **Baseline Data**

For Snapshot customers that opt-in to the study, Progressive will extract demographic data on the participant's age, marital status, gender, occupation, highest educational level, residential ZIP code, and urban, suburban, rural classification of the residential ZIP code (Kolko 2015).

## **Survey**

After participants opt-in to the study, they will be prompted to complete an intake survey hosted by Truemotion. This will collect data on their vehicle characteristics (e.g. Bluetooth connectivity, GPS navigation), driving history (e.g. length of licensure), self-reported phone use while driving, perceptions of level phone use relative to others like them, use of settings to limit distracted driving (e.g. Do Not Disturb While Driving), and general behavioral characteristics (e.g. 5-trial delay discounting scale).

## **2.9. Allocation to Treatment**

Progressive Snapshot users that opt-in to participate will be added to a study list tracked by TrueMotion. 3,000 participants have enrolled into the study, they will complete an intake survey, collecting information about driving history, demographics, and behavioral characteristics. Simple individual-level randomization will be used. TrueMotion will use a random number generator to randomize each user that opts in to 1 of the 6 arms: (Arm 1) control, (Arm 2) social comparison feedback, (Arm 3) end of rating period incentive, (Arm 4) end of rating period incentive and social comparison feedback (Arm 5) weekly loss framed incentive and social comparison feedback, (Arm 6) larger weekly loss framed incentive and social comparison feedback. Intervention will be delivered by TrueMotion through the Snapshot mobile app to the study participants. Additionally, iPhone users in all arms will get push notifications prompting them to activate the Do Not Disturb While Driving setting on iPhones.

## **2.10. Behavioral Interventions**

### **2.10.1. Intervention Arms**

Intervention Arm	Notifications	Incentive	
		Timing	Size
Driver Mode Nudge (all arms, iPhone users only)	3 times over 3 weeks: Prompt to enable Do Not Disturb While Driving. Linked to website with instructions and frequently asked questions: www.besafir.org/do-not-disturb .  Sample messages: Arms 1-2: "Reduce annoying notifications when driving (while keeping the urgent ones!). Enable Do Not Disturb While Driving. Tap here to learn how!"  Arms 3-6: "Increase your chance to earn \$ and reduce annoying notifications when driving (while keeping the urgent ones!). Enable Do Not Disturb While Driving. Tap here to learn how!"	N/A	N/A
1. Control (monitor only)	Continue in monitoring only mode	N/A	N/A
2. Social comparison feedback	Initial push notification: Told they will be compared to drivers like them each week and that they will receive up to 3 stars.	N/A	N/A

	
Weekly push notification:
 
a. Compare phone use % relative to Progressive Snapshot customers like them based (age, sex, marital status, urban/suburban/rural residence). Told can receive up to three stars.
 
 
• 1 star (if <50th percentile)
 
• 2 stars (if <math>\geq</math> 50th percentile, <90th percentile)
 
• 3 stars if <math>\geq</math> 90th percentile (top performer)
 
 
Sample message: “★ ★ out of 3 stars. Almost there! You're better than at least half of our drivers at staying off your phone. A little less swiping, typing, and holding the phone and you'll be one of our best drivers! ”
		
3. End of rating period incentive	
Initial notification:
 
a. Financial Incentive: Tell them they have a chance to win \$50 in 50 days for keeping handheld phone use to a minimum.
 
 
• If <50th percentile), then paid \$0
 
• If <math>\geq</math> 50th percentile, <90th percentile), then paid \$25
 
• If <math>\geq</math> 90th percentile (top performer), then paid \$50
 
	Redeemed at end of rating period	Max: \$50 (\$1/day)
4. End of rating period incentive + social comparison feedback	
Initial notifications:
 
a. Social comparison feedback: Tell them they will be compared to drivers like them each week and that they will receive up to 3 stars.
 
b. Financial Incentive: Tell them they have a chance to win \$50 in 50 days for keeping handheld phone use to a minimum.
 
 
• If get 1 star (<50th percentile), then paid \$0
 
• If get 2 stars (<math>\geq</math> 50th percentile, <90th percentile), then paid \$25
 
• If get 3 stars <math>\geq</math> 90th percentile [top performer]), then paid \$50
 
 
Weekly push notifications:
 
a. Social Comparison - Compare to distribution for Progressive driver cohort (age, geographic area)
 
 
• 1 star (if <50th percentile)
 
• 2 stars (if <math>\geq</math> 50th percentile, <90th percentile)
 
• 3 stars if > 90th percentile (top performer)
 
	Redeemed at end of rating period	Max: \$50 (\$1/day)

	
e.g. “★ out of 3 stars. Not bad, but more than half of our drivers used their phone less than you this week. Less swiping, typing, and holding your phone and you can move up the ranks!”
 
b. Financial Incentive: Reminder regarding the potential to earn incentive at end of intervention period.
 
e.g. “Remember, you need to use your phone less than half our other drivers to earn \$ at the end of the study! Safety pays!”
 
c. Post- trip 0 seconds distraction notification (throttled): Each week, participant will receive a gain-framed message after the first driving trip with 0 seconds of phone use.
 
e.g. “Hey Now! You didn't swipe and type your phone while driving. Awesome! Keep up the great work to stay safe and be one our best drivers!”
		
5. Weekly loss-framed incentive + social comparison feedback	
Initial push notifications:
 
a. Social comparison feedback: Tell them they will be compared to drivers like them each week and that they will receive up to 3 stars.
 
b. Financial incentive: Tell participants they have \$1/day per coming to them over the next 50 days and that they will be paid each week. Told that they need to not use their phone while driving to keep from losing any money.
 
Weekly push notifications:
 
a. Social Comparison - Compare to distribution for Progressive driver cohort (age, geographic area)
 
1 star (if <50th percentile)
 
2 stars (if ≥ 50th percentile, <90th percentile)
 
3 stars if > 90th percentile (top performer)
 
Weekly push notifications:
 
b. Social Comparison - Compare to distribution for Progressive driver cohort (age, geographic area)
	Amount not lost for week delivered weekly	Max: \$50 (\$1/day)

	
1 star (if <50th percentile)      2 stars (if <math>\geq</math> 50th percentile, <90th percentile)      3 stars if <math>></math> 90th percentile (top performer)
 
e.g. “★ out of 3 stars. Not bad, but more than half of our drivers used their phone less than you this week. Less swiping, typing, and holding your phone and you can move up the ranks!”
 
b. Financial incentive: Amount of incentive received this week + total amount of money lost during study = [MONEYLOST].
 
 
• If get 1 star (if <50th percentile), then paid \$0
 
• If get 2 stars (if <math>></math> 50th percentile, <90th percentile), then get paid \$3.58
 
• If get 3 stars (if <math>></math> 90th percentile [top performer]), then get paid \$7.15
 
 
e.g. “You missed out on your weekly payment this week and a total of \$[MONEYLOST] so far this study. No worries, fresh start! Use your phone less to get ★★ and \$ next week! Safety pays!”
 
c. Post- trip 0 seconds distraction notification (throttled): Each week, participant will receive a gain-framed message after the first driving trip with 0 seconds of phone use.      e.g. “Hey Now! You didn't swipe and type your phone while driving. Awesome! Keep up the great work to stay safe and be one our best drivers!”
		
6. Larger weekly loss-framed incentive + social comparison feedback	
Initial push notifications:
 
 
Social comparison feedback: Tell them they will be compared to drivers like them each week and that they will receive up to 3 stars.
 
Financial incentive: Tell participants they have \$2/day per coming to them over the next 50 days and that they will be paid each week. Told that they need to not use their phone while driving to keep from losing any money.
 
 
Weekly push notifications:
 
 
Social Comparison - Compare to distribution for Progressive driver cohort (age, geographic area)
 
	Amount not lost for week delivered weekly	Max: \$100 (\$2/day)

	
 
• 1 star (if <50th percentile)
 
• 2 stars (if <math>\geq</math> 50th percentile, <90th percentile)
 
• 3 stars if > 90th percentile (top performer)
 
 
e.g. “★ out of 3 stars. Not bad, but more than half of our drivers used their phone less than you this week. Less swiping, typing, and holding your phone and you can move up the ranks!”
 
b. Financial incentive: Amount of incentive received this week + total amount of money lost during study = [MONEYLOST].
 
 
• If get 1 star (if <50th percentile), then paid \$0
 
• If get 2 stars (if > 50th percentile, <90th percentile), then get paid \$7.15
 
• If get 3 stars (if > 90th percentile [top performer]), then get paid \$14.29
 
 
e.g. “You missed out on your weekly payment this week and a total of \$[MONEYLOST] so far this study. No worries, fresh start! Use your phone less to get ★★ and \$ next week! Safety pays!”
 
c. Post- trip 0 seconds distraction notification (throttled): Each week, participant will receive a gain-framed message after the first driving trip with 0 seconds of phone use.
 
e.g. “Hey Now! You didn't swipe and type your phone while driving. Awesome! Keep up the great work to stay safe and be one our best drivers!”
		
--	--	--	--

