## 1.2. Sample Size, Power, and Minimum Detectable Differences

To have power of 0.80 to detect a clinically meaningful reduction of a 2% difference in amount of trip time spent actively using a phone (72 seconds/hour of driving), the minimum sample size is 1,842 (301 per arm).

With a target sample size of 3,000 and power of 0.80, we should be able to detect a difference between treatment arms of 52 seconds/hour of driving (i.e. an absolute reduction in phone use % of 1.44%). We would have a power of 0.94 to detect a difference of 60 seconds/hour of driving.

Proposed variables to be considered as effect modifiers in the primary analysis
1. iPhone vs. Android. Hypothesis: the relative reductions in active handheld phone use will be greater among those with iPhones due to the notification to encourage Do Not Disturb While Driving.
2. Quartile of baseline period active phone use % (i.e. total active handheld phone use seconds / total trip seconds). Hypothesis: the relative reductions in active hand held phone use while be greater among those in the highest quartile of baseline phone use due to greatest opportunity for improvement and least opportunity for improvement in the lowest quartiles.
3. Proportion of period active phone use % due to handheld calls vs. handheld non-call use. Hypothesis: the relative reductions in active hand held phone use while be greater among those with a greater proportion of handheld phone use due handheld call use vs. non-call use due to multiple available technological means to switch to handsfree calls.
4. Proposed variables to be considered as effect modifiers in hypothesis generating secondary analyses
5. Baseline use of automated Do Not Disturb While Driving setting (Y/N)
6. Baseline use of a phone mount
7. Mean hours of driving/week during baseline period
8. Age
9. Sex
10. Marital status
11. Urban-suburban-rural residence
12. Residence in state with universal handheld ban
13. Income
14. Education level

15. Number of prior traffic violations in prior 5 years
16. Number of car crashes in prior 5 years
17. Self-reported frequency of types of handheld phone use while driving (e.g. phone call, text messaging, adjusting navigation app, changing music app, social media app)
18. Willingness to give up phone use while driving scale
19. Automaticity scale of phone use while driving
20. Compulsive phone use scale
21. Delay discounting rate

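### The iPhone-only Do Not Disturb prompt mentions earning money in Arms 3-6 but not in Arms 1-2, so a larger iPhone effect in contrasts 2-7 cannot be read as an effect of the Do Not Disturb prompt

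*Combined protocol and SAP*

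**What the plan says.** Protocol section 2.9 describes the prompt as common to the trial: "iPhone users in all arms will get push notifications prompting them to activate the Do Not Disturb While Driving setting on iPhones". The intervention table in section 2.10.1 lists it as "Driver Mode Nudge (all arms, iPhone users only") and gives the schedule as "3 times over 3 weeks: Prompt to enable Do Not Disturb While Driving". Section 2.11 confirms that control-arm iPhone users get it too.

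The same table row prints two sample texts. Arms 1-2 get "Reduce annoying notifications when driving (while keeping the urgent ones!). Enable Do Not Disturb While Driving". Arms 3-6 get "Increase your chance to earn \$ and reduce annoying notifications when driving (while keeping the urgent ones", followed by the same instruction to enable the setting.

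Other incentive messages in the table do not depend on phone type:
- Arm 3 has one initial notification: "Tell them they have a chance to win \$50 in 50 days for keeping handheld phone use to a minimum". No weekly message is listed.
- Arm 4 has the initial notification plus a weekly message: "Reminder regarding the potential to earn incentive at end of intervention period".
- Arms 5 and 6 have an initial notification plus a weekly message giving that week's payment and the running loss.

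SAP section 1.2 puts phone type first among the effect modifiers for the primary analysis. Its hypothesis is that relative reductions "will be greater among those with iPhones due to the notification to encourage Do Not Disturb While Driving". SAP section 1.3 applies the analysis to all ten contrasts and says that it will allow the effectiveness of the prompts to be estimated. Neither section mentions that the wording differs by arm.

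**The concern.** A prompt that serves as background should be the same in every arm. This one also works as an incentive reminder in four arms, and only one phone group receives it. Within Arms 3-6, exposure to incentive messages therefore depends on phone type.

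The protocol gives no ground for treating the extra line as inert. Its rationale (section 1.2) names the frequency and visibility of incentives as levers for changing behavior. If the reminders work at all, they push the phone-type interaction in the direction that the SAP predicts. A result produced by reminders about money could then be reported as support for the Do Not Disturb prompt, in an analysis that the SAP classes as primary.

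**Working it through.** **1. Which contrasts compare different prompt texts.** SAP section 1.1 lists ten contrasts. As arm pairs, in order, they are 2v1, 3v1, 4v1, 5v1, 6v1, 3v2, 4v2, 4v3, 5v4 and 6v5, which reproduces the plan's count of ten. The text differs when one arm is 1 or 2 and the other is 3 to 6. That holds for contrasts 2, 3, 4, 5, 6 and 7, or 6 of 10. Contrasts 1, 8, 9 and 10 have the same text on both sides.

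**2. Incentive messages by phone type.** The intervention lasts 50 days, and 50 / 7 = 7.1, so take seven full weeks.

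| Arm | Android | iPhone | Ratio |
|---|---|---|---|
| 1-2 | 0 | 0 | – |
| 3 | 1 initial = 1 | 1 + 3 prompts = 4 | 4.0 |
| 4-6 | 1 initial + 7 weekly = 8 | 8 + 3 prompts = 11 | 1.4 |

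Protocol section 8.2 adds an arm-assignment email to all participants, which covers how they will be paid. The documents do not say whether this is the table's initial notification. If it is separate, Arm 3 becomes 2 against 5 (ratio 2.5) and Arms 4-6 become 9 against 12 (ratio 1.3). The difference of three messages is the same either way.

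**3. What the phone-type interaction measures.** Take a contrast of arm *a* (3 to 6) with arm *b* (1 or 2), with effects on one additive scale. Let T be the effect of the rest of the arm's package relative to arm *b*, D the effect of the Do Not Disturb request in iPhone users, and M the effect of the money line.

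- iPhone difference between arms: T(iPhone) + D(a) − D(b) + M
- Android difference between arms: T(Android)
- Interaction: [T(iPhone) − T(Android)] + [D(a) − D(b)] + M

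Two results follow. First, M enters the interaction in full and cannot be separated from the other terms. Second, if the request works equally well in both arms, D cancels, because both arms received it. Identical wording sets M to zero and takes the mismatched contrasts from 6 of 10 to 0 of 10, but it does not recover D. What remains is any difference between arms in how well the request works, mixed with any difference between iPhone and Android users in their response to the rest of the package. Phone type is chosen by the user, so the latter need not be zero.

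**4. Possible size (assumption only).** The documents give neither an effect for the money line nor an iPhone share. Suppose that the line lowers use by 5 to 20 s/h in iPhone users, and that 40% to 70% of participants have iPhones.

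- Shift in the overall contrast = share × effect: 0.40 × 5 = 2 s/h to 0.70 × 20 = 14 s/h. Against the detectable difference of 52 s/h in SAP section 1.2, that is 4% to 27%.
- Shift in the iPhone-minus-Android difference = the full 5 to 20 s/h.

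**The case against.** A reader might infer that six of the ten contrasts are biased. The documents do not support that. Section 2.9 uses simple individual randomization and the wording is fixed by arm, so the money line is part of what each arm was assigned. The overall contrasts estimate the package as delivered, averaged over phone types, as any overall effect is. Phone type is also a covariate (SAP section 1.1), and its modification of the effect will be examined. This part of the objection stands in full.

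It also stands that the protocol prints both texts openly, that they are labelled as samples, and that a larger iPhone effect could, but need not, come from the reminders. In Arms 5-6, where payments themselves arrive weekly, three more mentions of money add little.

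A further defense is the mediation analysis in SAP section 1.3, which asks whether activating an automated setting explains the outcome by arm and phone type. It does not remove the problem. One message both requests the setting and recalls the money, so the money line may raise activation as well as act directly on phone use.

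The last objection is that identical wording would still leave the prompt's effect unidentified. Step 3 agrees. That is a reason to correct the SAP's interpretation as well as the wording. It does not justify keeping a removable alternative explanation.

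Equal wording is not quite equal effect either. The same three prompts are a larger relative addition in Arm 3 than in Arm 4, so contrast 8 could be slightly affected.

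**Conclusion.** The point holds as a problem of attribution in a pre-specified primary effect-modifier analysis. In contrasts 2-7 the arm-by-phone interaction mixes extra incentive reminders with whatever the Do Not Disturb request contributes. SAP sections 1.2 and 1.3 therefore cannot read it as they do. The exposure gap is most material in Arm 3, which makes contrasts 2 and 6 the most affected, and it is small in Arms 4-6.

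This rests on the sample texts having been used as printed and on the money line having some effect. The size of that effect is unknown, and the ranges in step 4 are illustrations. A separate limit does not depend on the wording: with no unprompted iPhone group and no randomization of phone type, the interaction does not estimate the prompt's effectiveness.

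**What to change.** If messages can still be changed, use the Arm 1-2 text in all six arms. Send any money reminder for Arms 3-6 as a separate notification to iPhone and Android users alike. The cost is one notification string per arm. The small downside is that iPhone users in Arms 3-6 lose the line that links the setting to the incentive.

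If the messages have already gone out, state in the SAP that the Arms 3-6 wording is part of the incentive package, and report contrasts 2-7 separately by phone type. The Android results are free of the prompt.

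In either case, withdraw the statement in SAP section 1.3 that the phone-type analysis estimates the effectiveness of the prompt, and remove the causal attribution from the hypothesis in section 1.2. These are text changes only and need no new data.
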